4.1.2.1 PRIMARY ENDPOINT

The primary endpoint is the proportion of PV participants having achieved CRmin (as assessed by the investigator) within 30 weeks. A stratified Cochran-Mantel-Haenszel (CMH) test will be calculated with the stratification factors of disease status, disease severity, and body weight at randomization.

Disease activity relative day will be calculated as specified in Section 2.2.3. Any CRmin achieved with a relative day up to day 218 is counted as a primary endpoint response. CRmin cases achieved for the first time after day 218 will not be considered.

The main analysis on the primary endpoint will use the ‘composite strategy’ approach in case of main intercurrent events. This strategy implies that when a main intercurrent event (ICE) occurs, a participant is considered a non-responder. This happens in the following situations:

	Statistical Analysis Plan	
ARGX-113-1904	Final analysis	Final 2.0 of 22NOV2023

- Intercurrent medications (see section 3.4.2) before CRmin
 - Immunosuppressants or dapsone at therapeutic doses for at least 4 weeks in total in the last 12 weeks before achieving CRmin
 - IVIg/SCIg at immunomodulating dose (≥ 1 g/kg/month) before achieving CRmin
 - Immunoabsorption or plasma exchange (at least 1 procedure) before achieving CRmin
 - Rituximab or other anti-CD20 biologics (at least 1 infusion) before achieving CRmin
 - IV or IM corticosteroids administered (at least 1 administration, any dose) once the participant has achieved minimal prednisone (or prednisone equivalent) dose of ≤ 10 mg/day (i.e., during the 8 week period required in the protocol to confirm the CRmin status) or administered at any moment before achieving CRmin in any of the three following situations:
 - a) more than 60 mg for 3 consecutive days
 - b) more than 40 mg for 4 consecutive days
 - c) more than 7 days in total
 - Tetracyclines administered at least 100 mg/day for at least 2 weeks in total in the last 10 weeks before achieving CRmin
 - Any interventional study drug under development for pemphigus given before achieving CRmin
- Discontinuation of IMP before CRmin due to lack of efficacy
- Death

The conditions on intercurrent medications above are tailored for the primary endpoint (CRmin). Conditions on intercurrent medications based on medication type, minimal dosing and minimal duration apply to the secondary endpoints below with composite strategy or hypothetical strategy. However, conditions on intercurrent medications like “in the last x weeks before achieving CRmin” are specific for CRmin only. Details on the derivation of intercurrent events are provided in Appendix 9.1.

Missing values for reasons other than the main intercurrent events, will be imputed as follows:

- all CR assessments missing: CRmin = non-response
- CRmin never ticked: CRmin = non-response
- CRmin is ticked but date of CRmin is missing: date for CRmin will be imputed by disease assessment visit date

A supplementary analysis for this primary analysis on mITT will use the ‘treatment policy strategy’ where the occurrence of the intercurrent event is considered irrelevant: CRmin as assessed by the investigator is used regardless of whether or not the intercurrent event occurs. Missing values for reasons other than the main intercurrent events will be handled as stated above for the primary estimand.

	Statistical Analysis Plan	
ARGX-113-1904	Final analysis	Final 2.0 of 22NOV2023

A landmark analysis will be performed as a supplementary analysis, i.e. proportion of PV participants having achieved CRmin (as assessed by the investigator) at 30 weeks (weeks 22-30 CR on minimal therapy). This implies that a responder is defined as a participant that is still in CR and on $\leq 10\text{mg/day}$ for at least 2 months (8 weeks), at week 30. Disease activity relative day will be calculated as specified in Section 2.2.3. If the disease status at week 30 analysis visit (see Section 2.2.4) is not missing, then that disease status will be used. If the disease status at week 30 analysis visit is missing but disease status at any analysis visits from week 26 to week 29 is not missing the last non-missing analysis visit assessment from week 26 will be used. If all disease status assessments at the analysis windows for week 26 to week 30 are missing, then CRmin at week 30 is No.

A ‘composite strategy’ approach for dealing with the ICEs will be applied. Accordingly, use of intercurrent medication or permanent IMP discontinuation due to lack of efficacy before or at week 30 will be considered as a non-responder regardless the outcome of the algorithm above.

Additionally, a sensitivity analysis on this landmark analysis will be performed as above without using the week 26 to week 29 data to impute any potential missing disease status at week 30.

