9.5.6. Primary Endpoint

The International Council for Harmonisation of Technical Requirements for Pharmaceuticals for Human Use [ICH] E9 (R1) provides further information on estimands and sensitivity analyses in clinical trials; ICH E9 (R1) came into effect on 30 Jul 2020 and follows below.

Definition of the Estimand for the Primary Endpoint

- Population: adult participants with moderate to severe PV newly diagnosed or experiencing flare, on add-on therapy of low doses of oral prednisone, and that are further defined by the inclusion (Section 5.1) and exclusion (Section 5.2) criteria.
- Variable: proportion of PV participants who achieve CRmin within 30 weeks
- Main intercurrent events (ICEs):
 1. Intercurrent medications before CRmin
 - a. Immunosuppressants or dapsons at therapeutic doses for at least 4 weeks
 - b. IVIg at immunomodulating dose (≥ 1 g/kg/month)
 - c. Immunoabsorption or plasma exchange
 - d. Rituximab or other anti-CD20 biologics
 - e. IV corticosteroids >200 mg cumulatively within 2 weeks
 2. Discontinuation of IMP before CRmin due to lack of efficacy
- Population-level summary: the strata-adjusted difference in the proportion of responders (95% CI) between efgartigimod PH20 SC in combination with add-on therapy of low doses of oral prednisone and placebo in combination with add-on therapy of low doses of oral prednisone.

Handling of Main ICEs

A composite strategy approach will be taken to address both main ICEs. This implies that participants that take intercurrent medications before CRmin as specified previously, as well as participants that discontinue IMP before CRmin due to lack of efficacy, will be considered nonresponders for the primary endpoint analysis.

Estimation of Treatment Effect and Statistical Inference

The proportion of participants with PV having achieved CRmin within 30 weeks will be tested by means of a stratified Cochran-Mantel-Haenszel (CMH) test using the mITT population. The model will be stratified by disease status, disease severity, and body weight at randomization. The strata-adjusted difference of proportions will be presented with its 95% CI and 2-sided p-value. In addition, the odds ratio and its 95% CI will be provided.

Handling of Missing Data

Missing data for reason of 1 of the main ICEs will be handled as described above.

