4.1.2.2 KEY SECONDARY ENDPOINTS (ALPHA CONTROLLED)

The following key secondary endpoints, which will be tested in the mITT population in hierarchical order (see section 4.1.4), are defined as:

- 1) The proportion of PV+PF participants that have achieved CRmin within 30 weeks using the same stratified CMH as for the primary endpoint. As this first key secondary endpoint is similar to the primary endpoint, the same approach for handling the main ICEs (both composite strategy and treatment policy strategy), as suggested for the primary analysis, will be applied.
- 2) Normalised cumulative Prednisone dose (NCPD, mg/kg/day) over the whole planned treatment phase in PV participants, will be analyzed by an analysis of covariance (ANCOVA) model to compare both treatment groups. Only actual administrations of prednisone are considered (not as scheduled). The model will include treatment and the stratification variables will be considered as factors.

Main intercurrent events are handled using the hypothetical strategy, that is, as follows:

- Intercurrent medications (see section 3.4.2): stop calculating cumulative dose after ICE. In case 'immunosuppressants for at least 4 weeks in total' is the ICE, use end of the 4 weeks IC medication as stop for cumulative dose calculation. In case ‘tetracyclines for at least 2 weeks in total' is the ICE, use end of the 2 weeks IC medication as stop for cumulative dose calculation. In case ‘IV or IM corticosteroids ' is the ICE, use the first day of this IC medication as stop for cumulative dose calculation.
- Discontinuation of IMP before CRmin due to lack of efficacy: stop calculating cumulative dose after this ICE.

Details on the derivation of intercurrent events are provided in Appendix 9.1.

	Statistical Analysis Plan	
ARGX-113-1904	Final analysis	Final 2.0 of 22NOV2023

A non-parametric stratified Mann-Whitney test will be performed as sensitivity analysis.

A supplementary analysis for this secondary endpoint will use the ‘treatment policy strategy’ where the occurrence of the intercurrent event is considered irrelevant: NCPD is calculated regardless of whether or not the intercurrent event occurs.

3) Time to CR in PV participants, calculated as the difference between the first date CR was achieved and the first IMP administration date.

Time to CR (days) = date (first CR) - first IMP date + 1

Main intercurrent events are handled as follows (composite strategy):

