9. APPENDICES

9.1 MAIN INTERCURRENT EVENTS (ICE)

The conditions below are tailored for the primary endpoint (CRmin). Conditions based on medication type, minimal dosing and minimal duration apply to the other endpoints with composite strategy or hypothetical strategy. However, conditions like “in the last 12 weeks before achieving CRmin” are specific for CRmin only. For these strategies, NCPD is calculated until and excluding the first day of ICE unless specified otherwise.

9.1.1 *Immunosuppressants or dapsone at therapeutic doses for at least 4 weeks in total in the last 12 weeks before achieving CRmin*

- Azathioprine, at least 1 mg/kg/day
- Mycophenolate mofetil, at least 2 g/day
- Mycophenolic acid, at least 1000 mg/day
- Mycophenolate mofetil hydrochloride, at least 2 g/day
- Cyclophosphamide, at least 1 mg/kg/day, or IV pulse 500 mg/month
- Methotrexate (sodium), at least 5 mg/week (in Japan), whereas 10 mg/week in Europe
- Ciclosporin, at least 3 mg/kg/day
- Dapsone, at least 1 mg/kg/day
- Hydroxychloroquine sulfate, at least 400mg/day
- Thalidomide, at least 50mg/day

For CRmin and time to CRmin these events should occur in the last 12 weeks before CRmin to be considered as an ICE. NCPD is calculated until and including the last day of the applicable 4 weeks intake.

9.1.2 *IVIg/SCIg at immunomodulating dose (≥ 1 g/kg/month) before achieving CRmin*

- ‘Immunoglobulins NOS’ or ‘Immunoglobulin G Human’ or ‘Immunoglobulins’ or ‘Immunoglobulin Human Normal’ or ‘Anti-D Immunoglobulin
and cmroute=’INTRA VENOUS’ or ‘SUBCUTANEOUS’.

9.1.3 *Immunoabsorption or plasma exchange (at least 1 procedure) before achieving CRmin*

- ‘Plasmapheresis’ or ‘Immunoabsorption therapy’ as PRDECOD, at least one cycle

	Statistical Analysis Plan	
ARGX-113-1904	Final analysis	Final 2.0 of 22NOV2023

9.1.4 *Rituximab or other anti-CD20 biologics (at least 1 infusion) before achieving CRmin*

- Rituximab, at least one cycle of 1 g or 375 mg/m²
- Obinutuzumab
- Ofatumumab
- Ocrelizumab
- Ibritumomab tiuxetan
- Veltuzumab
- Tocilizumab

9.1.5 *IV or IM corticosteroids*

- administered (at least 1 administration, any dose) once the participant has achieved minimal prednisone (or prednisone equivalent) dose of ≤ 10 mg/day (i.e., during the 8 week period required in the protocol to confirm the CRmin status) or administered at any moment before achieving CRmin in any of the three following situations:
 - a) more than 60 mg of prednisone equivalent for 3 consecutive days

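### The SAP alters two of the protocol's non-response rules for the primary endpoint without declaring the change, and no planned analysis clearly tests CRmin within 30 weeks under the protocol's rules

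*SAP*

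**What the plan says.** Protocol 9.5.6 lists the intercurrent medications that, if taken before CRmin, make a participant a non-responder under the composite strategy. Two of them are "Immunosuppressants or dapsons at therapeutic doses for at least 4 weeks" and "IV corticosteroids >200 mg cumulatively within 2 weeks". Neither has a look-back limit other than CRmin itself.

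SAP 4.1.2.1 defines the same two events differently.

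- **Immunosuppressants and dapsone:** "Immunosuppressants or dapsone at therapeutic doses for at least 4 weeks in total in the last 12 weeks before achieving CRmin". Appendix 9.1.1 shows that the window is deliberate: "For CRmin and time to CRmin these events should occur in the last 12 weeks before CRmin to be considered as an ICE".
- **Corticosteroids:** the 200 mg rule does not appear. Any IV or IM dose counts once the participant has reached 10 mg/day or less of prednisone. Before that, a dose counts if "administered at any moment before achieving CRmin in any of the three following situations": (a) "more than 60 mg for 3 consecutive days", (b) over 40 mg for 4 consecutive days, or (c) over 7 days altogether. Appendix 9.1.5 supplies the unit missing from the main text: "more than 60 mg of prednisone equivalent for 3 consecutive days".

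For CRmin in PV+PF participants, SAP 4.1.2.2 carries these rules over: "As this first key secondary endpoint is similar to the primary endpoint, the same approach for handling the main ICEs" is applied.

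SAP 6.1 lists the changes from the protocol. On intercurrent events it restates the protocol's medications by class, without durations or dose limits, and declares two additions only: tetracyclines and pemphigus drugs under development. Protocol section 9 allows minor changes of method without an amendment but says that they will be recorded in the SAP as changes from the protocol.

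**The concern.** These rules decide who is a responder on the endpoint that gates the whole testing sequence, and on the next endpoint in it. Protocol 9.5.7 leaves intercurrent-event details to the SAP only for the second to fourth key secondary endpoints. For the primary endpoint the protocol fixes the events itself. Someone who reads SAP 6.1 would conclude that, apart from two added drug classes, the protocol's definitions still hold.

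Both drug groups are prohibited during the trial (Protocol 6.8.2), and Protocol 2.1 credits immunosuppressants with reducing prednisone consumption. CRmin requires prednisone at 10 mg/day or less, so use before the window could bear on the endpoint. If the two rule sets classify anyone differently, the trial report would have no result for the endpoint as the protocol defined it.

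**Working it through.** The plan gives no figure for this point, so there is none to reproduce. The check sets the two rule sets side by side and classifies example exposures. The exposures are illustrations, not data from the documents.

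**Time outside the window.** Twelve weeks is 84 days. Protocol 4.2 expects CRmin at weeks 24 to 30 for most participants on active treatment, and SAP 4.1.2.1 accepts CRmin up to day 218. Uncounted days = (CRmin day − 1) − 84.

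- Week 24 (day 169): 168 − 84 = 84 of 168 days, 50%.
- Week 30 (day 211): 210 − 84 = 126 of 210 days, 60%.
- Day 218: 217 − 84 = 133 of 217 days, 61%.

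**Classification.** Items (a) and (b) are read as daily doses. The SAP's equivalence factors (section 3.5.2) are prednisone 10 and methylprednisolone 8.

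| Exposure before CRmin | Protocol 9.5.6 | SAP 4.1.2.1 |
|---|---|---|
| Immunosuppressant at therapeutic dose on days 57 to 84 (28 days), CRmin on day 169 | Non-responder | No event: the window is days 85 to 168 |
| 2 × 125 mg IV methylprednisolone before the 10 mg/day phase | Non-responder: 250 mg, or 250 × 10/8 = 312.5 mg prednisone equivalent, both above 200 | No event: 2 days meet none of (a), (b), (c) |
| IV corticosteroid, 3 consecutive days at 61 mg prednisone equivalent | No event if the 200 mg is in prednisone equivalents: 3 × 61 = 183 mg | Non-responder under (a) |
| One IM dose during the 10 mg/day phase | No event: IV route only | Non-responder |

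The first two rows are looser in the SAP and the last two stricter, so neither rule set contains the other. The third row depends on a unit that the protocol does not state. The second row does not.

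**Whether a planned analysis recovers the protocol's rules.**

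- The treatment-policy analysis ignores all intercurrent events.
- The per-protocol and Ukraine-excluded repeats use the primary estimand only (SAP 4.1.2), so they keep the SAP's rules. Per-protocol would remove an affected participant, if the use is graded a major deviation, but would not count that participant as a non-responder.
- The landmark analysis and its sensitivity version count intercurrent medication up to week 30 without saying whether the 12-week window applies. SAP 3.4.2 lists immunosuppressants without a window (and without dapsone) and IV or IM corticosteroids without thresholds. Whichever applies, the response tested is status at week 30, not CRmin within 30 weeks.
- Table 14.1.2.7 and listing 16.2.4.6 show the therapies but do not re-test response.

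**Scale per case.** Assume 183 PV participants split 2:1, that is 122 and 61. One reclassified participant moves the crude response rate by 1/122 = 0.8 points on efgartigimod or 1/61 = 1.6 points on placebo. The documents give no expected number of cases.

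**The case against.** The best defence is that this is a documentation gap. The new rules are printed in full in SAP 4.1.2.1 and Appendix 9.1, and the SAP says that they are tailored to CRmin. The protocol's version cannot be programmed as it stands: it does not define a therapeutic dose or give a unit for the 200 mg, so the SAP had to add detail. The drugs are prohibited, so cases may be few. Serious use may be excluded from the per-protocol set, and on one reading the landmark analysis is at least as strict as the protocol for corticosteroids and for immunosuppressants other than dapsone. The protocol promised supplementary analyses under other strategies, not under other definitions.

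Much of this stands. A reader might infer concealment; the documents do not support that, because the rules are in plain view and only the declaration is missing. A reader might also see a three-way ambiguity in the corticosteroid doses. Read as totals over any 3 or 4 days, however, (a) would be redundant, since any 3-day total above 60 mg is also a 4-day total above 40 mg. Daily dose is the sensible reading, and the appendix settles the unit. The SAP's listing of death adds little, because someone who dies before CRmin is already a non-responder.

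Two things remain. Supplying a unit does not explain a 12-week window or the removal of a cumulative limit. And no existing analysis clearly re-tests the primary response under the protocol's definitions.

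**Conclusion.** The point holds as an undeclared change to two non-response rules, with no planned analysis that clearly shows whether it matters. It affects CRmin within 30 weeks in PV (primary) and in PV+PF (first key secondary). It does not invalidate the primary analysis, but it should be fixed before unblinding.

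The size and direction of any effect are unknown, because the documents do not say how often such use is expected. A reader might infer that the change favours efgartigimod. The documents do not support that: the rules move both ways, and if prohibited use were commoner on placebo (an assumption), the looser window would add placebo responders. Nor is the uncounted 50% to 61% of time an effect size. It matters only if a participant takes a prohibited drug for 4 weeks or more in that period and still reaches CRmin.

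The conclusion assumes that the protocol's phrase about medication before CRmin sets no other look-back limit, and that (a) and (b) are daily doses.

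**What to change.** Before unblinding:

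1. Add a sensitivity analysis of the primary endpoint (PV) and the first key secondary endpoint (PV+PF) using the intercurrent-event definitions of Protocol 9.5.6, and state the unit used for the 200 mg.
2. List the immunosuppressant/dapsone change and the corticosteroid change in SAP 6.1, each with a rationale.
3. State whether the 12-week window applies to the landmark analysis.

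The SAP's rules can stay as the primary analysis. The two documents need to be reconciled openly; nothing here endorses either set of thresholds. The cost is a few lines of SAP text, one alternative event flag and two extra tables. If use is rare and the results agree, the tables will show it.

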4.1.2.2 KEY SECONDARY ENDPOINTS (ALPHA CONTROLLED)

The following key secondary endpoints, which will be tested in the mITT population in hierarchical order (see section 4.1.4), are defined as:

- 1) The proportion of PV+PF participants that have achieved CRmin within 30 weeks using the same stratified CMH as for the primary endpoint. As this first key secondary endpoint is similar to the primary endpoint, the same approach for handling the main ICEs (both composite strategy and treatment policy strategy), as suggested for the primary analysis, will be applied.
- 2) Normalised cumulative Prednisone dose (NCPD, mg/kg/day) over the whole planned treatment phase in PV participants, will be analyzed by an analysis of covariance (ANCOVA) model to compare both treatment groups. Only actual administrations of prednisone are considered (not as scheduled). The model will include treatment and the stratification variables will be considered as factors.

Main intercurrent events are handled using the hypothetical strategy, that is, as follows:

- Intercurrent medications (see section 3.4.2): stop calculating cumulative dose after ICE. In case 'immunosuppressants for at least 4 weeks in total' is the ICE, use end of the 4 weeks IC medication as stop for cumulative dose calculation. In case ‘tetracyclines for at least 2 weeks in total' is the ICE, use end of the 2 weeks IC medication as stop for cumulative dose calculation. In case ‘IV or IM corticosteroids ' is the ICE, use the first day of this IC medication as stop for cumulative dose calculation.
- Discontinuation of IMP before CRmin due to lack of efficacy: stop calculating cumulative dose after this ICE.

Details on the derivation of intercurrent events are provided in Appendix 9.1.

	Statistical Analysis Plan	
ARGX-113-1904	Final analysis	Final 2.0 of 22NOV2023

A non-parametric stratified Mann-Whitney test will be performed as sensitivity analysis.

A supplementary analysis for this secondary endpoint will use the ‘treatment policy strategy’ where the occurrence of the intercurrent event is considered irrelevant: NCPD is calculated regardless of whether or not the intercurrent event occurs.

3) Time to CR in PV participants, calculated as the difference between the first date CR was achieved and the first IMP administration date.

Time to CR (days) = date (first CR) - first IMP date + 1

Main intercurrent events are handled as follows (composite strategy):

- Intercurrent medications (see section 3.4.2) before CR: participant is assumed to not reach CR until the theoretical end of the study and is censored at day 218.
- Discontinuation of IMP before CR due to lack of efficacy: participant is assumed to not reach CR until the theoretical end of the study and is censored at day 218.

Participants without any disease assessment are censored at day 1. Participants with disease assessment but not achieving CR in the period from Day 1 to Day 218 and without intercurrent event in that period are censored at the earliest of day 218 and the end of treatment + FU phase.

A supplementary analysis for this secondary endpoint will use the ‘treatment policy strategy’ where the occurrence of the intercurrent event is considered irrelevant: Time to CR is calculated regardless of whether or not the intercurrent event occurs.

4) Time to DC in PV participants, calculated as the difference between the first date DC was achieved and the first IMP administration date. Similar calculations, ICE handling and censoring rules are applied as for ‘time to CR’ (composite strategy).

A supplementary analysis for this secondary endpoint will use the ‘treatment policy strategy’ where the occurrence of the intercurrent event is considered irrelevant: time to DC is calculated regardless of whether or not the intercurrent event occurs.

Both time to event endpoints will be statistically evaluated using the stratified Fleming-Harrington weighted logrank statistic FH (1,0), with the stratification factors disease status, disease severity, and body weight at randomization. For both, Kaplan-Meier survival plots by treatment arm will be produced (as in-text figures only).

5) NCPD over the whole planned treatment phase in all participants: same derivation as second key secondary endpoint (composite strategy and treatment policy strategy) but for all participants.

6) Time to DC in all participants: same derivation as fourth key secondary endpoint (composite strategy) but for all participants.

7) Time to CR in all participants: same derivation as third key secondary endpoint (composite strategy) but for all participants.

	
Statistical Analysis Plan
	

ARGX-113-1904
	
Final analysis
	
Final 2.0 of 22NOV2023

